#### 3.3 DESCRIPTION OF THE STUDY DESIGN

This is a Phase I/IIa randomized, double-masked, dose-ranging study designed to evaluate the safety and tolerability of TRS01 eye drops [REDACTED] in subjects with active non-infectious anterior uveitis.

Potential study subjects will be required to sign an informed consent document and meet all inclusion/exclusion criteria.

Eligible subjects will be randomized to treatment as follows:

- [REDACTED]
- [REDACTED]

Once it is determined that all eligibility criteria have been met subjects will be enrolled and treated with one of two concentrations of TRS01 in a 1:1 ratio. Approximately 20 eligible subjects will be enrolled at approximately two sites.

Study subjects will administer the randomly assigned treatment 4 times a day (QID) for 28 days. All study subjects will return for examination on Weeks 1, 2, 3 and 4 (Treatment Phase) with post-treatment evaluations (Follow-Up Phase) at Weeks 7 and Week 10. Figure 1: Study Schematic summarizes the study phases, anticipated visits and number of subjects at each phase and Appendix 1 summarizes the schedule of assessments from Screening through Week 10.

Treatment assignments will be masked to Tarsius, study subjects, Investigators, and site staff. In order to prevent unmasking, all study medications during the Treatment Period will be supplied in identical packages.

[figure not shown]
Randomization is employed as an unbiased method of assigning subjects to two groups in equal allocation (1:1 ratio).

Visits:

[figure not shown]
1. Visit 1/Day 1 – Screening/Randomization: Initial screening for eligibility and randomization to treatment. Subjects who meet the qualification criteria with anterior chamber cells Grade [REDACTED] in the study eye will be randomized and will initiate dosing with IP. The subject's first dose will occur after randomization under the observation of an unmasked staff member.
  - 1.1. [REDACTED] post first dose, AEs, if any, will be recorded. Subjects will be given one bottle of IP and instructed to dose at the remaining time points for that day (midday, afternoon, and evening if appropriate) and to begin dosing four times a day on the following day and onward.
2. Visit 2/Week 1 – Evaluation [REDACTED].
3. Visit 3/Week 2 – Evaluation [REDACTED].
4. Visit 4/Week 3 – Evaluation [REDACTED].
5. Visit 5/Week 4 – Conclusion of 28 days of dosing/treatment phase, [REDACTED].
6. Visit 6/Week 7 – Evaluation

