#### 9.1.3 Analysis of Efficacy

Efficacy measures will be ACC and flare.

Both Investigator-rated ACC and flare data will be assessed as a change from baseline (Visit 1/Day 1) Weeks 1 through 4 and a descriptive comparison of the two active treatment groups will be performed.

If available, anterior chamber SD-OCT cell data will be assessed as a change from baseline (Visit 1/Day 1) on Weeks 1 through 4 and a descriptive comparison of the two active treatment groups will be performed.

Changes in subject-rated ocular pain assessment on Weeks 1 through 4 will be evaluated via a descriptive comparison between the two active treatment groups.

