## **9.2 SAMPLE SIZE ESTIMATION**

This is a Phase I/IIa clinical study to evaluate the safety and tolerability of TRS01 with the sample size of up to 20 randomized subjects, across approximately 2 sites, as proposed by Tarsius. No formal sample size estimation was undertaken as this trial is exploratory in nature.

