## **9.3 LEVEL OF SIGNIFICANCE**

Level of significance to be outlined in the Statistical Analysis Plan.

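### Section 9.1.3 compares the two concentrations on unadjusted change in ACC and flare, so a chance baseline imbalance at about 10 per arm can tilt the exploratory dose contrast; a baseline-adjusted estimate beside it would cost little

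*Combined protocol and SAP*

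**What the plan says.** Section 9.1.3 opens with "Efficacy measures will be ACC and flare". It continues: "Both Investigator-rated ACC and flare data will be assessed as a change from baseline (Visit 1/Day 1) Weeks 1 through 4", and then "a descriptive comparison of the two active treatment groups will be performed". It names no covariate, stratum, shift table or interval. It also does not say whether a change in grade is to be summarized as a mean or by category.

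On size and allocation, section 9.2 gives "sample size of up to 20 randomized subjects, across approximately 2 sites" and adds "No formal sample size estimation was undertaken as this trial is exploratory in nature". Section 3.3 states "Randomization is employed as an unbiased method of assigning subjects to two groups in equal allocation (1:1 ratio"). The visible randomization text (sections 3.3, 3.3.2 and 4.2.1) mentions no stratification by grade, but part of 4.2.1 is redacted. Under section 5.2, subjects who withdraw are not replaced.

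Several other places bear on the point:
- Section 9.1 promises listings of all data by treatment, subject and visit, and defers the analyses to a Statistical Analysis Plan.
- Section 9.1.1 summarizes background variables by arm without naming baseline ACC or flare.
- Section 9.1.2 summarizes slit-lamp assessments as safety outcomes.
- Section 9.3 says only "Level of significance to be outlined in the Statistical Analysis Plan".
- Section 2 makes preliminary efficacy an exploratory objective; the primary objective is safety and tolerability.

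**The concern.** Change from baseline subtracts the whole of the baseline value. That is the right amount only if follow-up rises one for one with baseline. If the slope is below 1, change still depends on where the eye started, and eyes that enter worse fall further on average. A slope below 1 is plausible here: subjects enter with active disease, and the study eye is the one with the higher ACC grade (Synopsis), so some regression toward the mean is to be expected.

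Both arms are active and the study is described as dose-ranging, so the contrast between concentrations is its only randomized information on efficacy. With about 10 eyes per arm, mean baseline grade can differ noticeably by chance. A reader choosing between concentrations from the raw change could credit to the dose what belongs to the starting grade.

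**Working it through.** The plan states no power, effect size, SD or correlation, so it has no figure of its own to reproduce.

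**Inputs.** Up to 20 subjects at 1:1 gives n = 10 per arm (sections 9.2 and 3.3). Assumed, because the documents do not give them: the baseline-follow-up correlation rho, and k, the ratio of follow-up SD to baseline SD. The baseline SD is s. Scores are treated as roughly normal and summarized by means.

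**Step 1: chance imbalance.** The SD of the difference in baseline means is s × sqrt(2/10) = 0.447s. The probability that it exceeds 0.5s in either direction is 2 × (1 − Φ(0.5/0.447)) = 0.26; for 0.75s it is 0.09. If s were 0.5, 0.75 or 1.0 grade (assumed), 0.447s would be 0.22, 0.34 or 0.45 grade.

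**Step 2: carry-over.** The slope of follow-up on baseline is rho × k, so the share of the imbalance that passes into the change contrast is 1 − rho × k. With k = 1, an imbalance of 0.5s shifts the contrast by 0.5 × 0.5s = 0.25s at rho 0.5, and by 0.7 × 0.5s = 0.35s at rho 0.3.

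**Step 3: how often the worse-starting arm looks better.** With k = 1 and no true difference, the correlation between the baseline difference and the size of the fall is r = sqrt((1 − rho)/2). The probability that the worse-starting arm shows the larger fall, averaged over imbalances of every size, is 1/2 + arcsin(r)/π.
- rho 0.5: r = 0.500, probability 0.67.
- rho 0.3: r = 0.592, probability 0.70.

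Without the dependence on baseline it would be 0.50.

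**Step 4: precision.** In units of s², the variance per subject is 1 + k² − 2 × rho × k for raw change and k²(1 − rho²) after adjustment. Estimating the slope from 20 subjects multiplies the adjusted variance by about 1 + 1/16 = 17/16 and uses one degree of freedom (t quantile 2.110 on 17 df against 2.101 on 18). Relative interval width is sqrt(variance ratio × 17/16) × 2.110/2.101.

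| k | rho | Carry-over | Variance ratio | Relative width |
|---|---|---|---|---|
| 1 | 0.3 | 0.70 | 0.65 | 0.83 |
| 1 | 0.5 | 0.50 | 0.75 | 0.90 |
| 1 | 0.7 | 0.30 | 0.85 | 0.95 |
| 1 | 0.9 | 0.10 | 0.95 | 1.01 |
| 1.5 | 0.3 | 0.55 | 0.87 | 0.97 |
| 1.5 | 0.5 | 0.25 | 0.96 | 1.02 |
| 2 | 0.5 | 0.00 | 1.00 | 1.04 |

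**Step 5: check on graded scores.** This was a simulation of 20,000 trials per scenario, 10 per arm, with no dose difference. Entry grades were drawn from assumed mixes of 2 to 4; 30% or 50% of eyes cleared outright and the rest fell by a binomial draw. Between 64% and 76% of the imbalance carried over. The imbalance explained 10% to 27% of the variance of the change contrast, and it reached at least 0.3 grade in 16% to 44% of trials. The mean contrast over all trials was zero to within simulation error. With a single entry grade there was no effect.

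**The case against.** The strongest reply is that the plan does use baseline: change from baseline subtracts it. That is correct. A reader might infer from the missing covariate that baseline grade is ignored, and the text does not support that. What remains is narrower: full subtraction is the wrong amount unless the slope is 1.

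Second, with at most 20 subjects the listings in section 9.1 will show every baseline and visit grade, and section 9.1.2 summarizes slit-lamp findings, which under section 8.1 include cells and flare. This stands as far as it goes: an imbalance could be found. But a listing does not correct a group contrast, and no visible text does so.

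Third, much is hidden. The ACC entry grade is redacted in section 3.3, the ACC scale is missing from 8.1.1.1, the flare scale is redacted in 8.1.2, part of 4.2.1 is redacted, and the separate SAP is not in the file. The statement that nothing adjusts for baseline therefore covers the visible protocol only. If ACC entry is limited to one grade the ACC effect disappears, although baseline flare could still vary.

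Fourth, equal SDs are a favourable assumption. An entry requirement can narrow the baseline spread while follow-up spreads out; as the table shows, carry-over then shrinks and the gain in precision can vanish. This stands in full.

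Finally, efficacy is exploratory and no test, decision rule or dose-selection rule depends on it in the visible text. This also stands, and it limits the weight of the point.

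**Conclusion.** The point holds as a modest, optional improvement to an exploratory analysis. It is not an error in the plan. Under equal SDs, an imbalance above 0.5 SD has 26% probability; 50% (rho 0.5) to 70% (rho 0.3) of it enters the dose contrast; and adjustment would narrow the interval by about 10% to 17% after paying for the slope. There is little or no gain in precision if follow-up SD exceeds baseline SD or if rho is high. These figures rest on assumed SDs and correlations and on 10 evaluable subjects per arm, which withdrawals could reduce.

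A reader might go further and infer that the comparison is biased, or that the arm starting worse will look like the better dose. Neither follows. Randomization makes the expected distortion zero over repeated trials, and the worse-starting arm shows the larger fall with probability 0.67 to 0.70, not with certainty.

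**What to change.** In section 9.1.3, or in the SAP if it is not already there, add for ACC and flare:

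1. A table of baseline grade by arm.
2. A shift table of baseline grade by visit grade, by arm, for Weeks 1 to 4. It keeps the ordinal scale and shows any floor effect without a model.
3. Beside the raw difference in mean change, the difference adjusted for baseline grade with a 95% CI, labelled descriptive. A linear adjustment of a short grade is an approximation, which is why it should stand next to the shift table and not replace it.

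Proportions at the clear grade with exact intervals are optional: clearing also depends on entry grade, so they do not correct an imbalance.

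The cost is a few tables for two measures at four visits and one simple model per measure and visit, all from data already scheduled in Appendix 1. No subject, visit, test or claim is added. Fixing the choice before unmasking avoids picking between raw and adjusted results afterwards. If the SAP or the redacted randomization text already deals with baseline grade, a reference to it in 9.1.3 is enough.

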## **9.2 SAMPLE SIZE ESTIMATION**

This is a Phase I/IIa clinical study to evaluate the safety and tolerability of TRS01 with the sample size of up to 20 randomized subjects, across approximately 2 sites, as proposed by Tarsius. No formal sample size estimation was undertaken as this trial is exploratory in nature.

## **9.3 LEVEL OF SIGNIFICANCE**

Level of significance to be outlined in the Statistical Analysis Plan.

## **9.4 PROCEDURE FOR ACCOUNTING FOR MISSING, UNUSED, OR SPURIOUS DATA**

Any missing, unused, or spurious data will be noted in the final clinical study report.

## **9.5 PROCEDURE FOR REPORTING DEVIATIONS FROM THE STATISTICAL PLAN**

Any deviations from the statistical analysis plan will be described and a justification given in the final clinical study report.

## **9.6 SUBJECTS TO BE INCLUDED IN THE ANALYSIS**

Intent-to-Treat (ITT) Population: The ITT population will include all randomized subjects who took at least 1 dose of investigational product. The Safety Population will include all randomized subjects.

Per Protocol (PP) Population: The PP population is a subset of the ITT population, which will include those subjects who did not have significant protocol deviations. The PP population will be defined and documented by the clinical study team and the biostatistician prior to database lock and unmasking of the subjects.

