**Unrelated:**

- Event occurring before dosing.
- Event easily explained by uveitis status.
- Event or intercurrent illness due wholly to factors other than investigational product use.

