##### 8.1.1.2 Spectral- Domain Optical Coherence Tomography

Anterior chamber SD-OCT imaging will be performed for the study eye on Visit 1/Day 1 after randomization (before first drop administration) and at each subsequent study visit, at select sites. [REDACTED]

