## 9 STATISTICS

### 9.1 STATISTICAL METHODS

Continuous measures (e.g., age) will be summarized descriptively by the mean, standard deviation, median, minimum and maximum values. Categorical measures will be summarized by the number and percent of subjects. The statistical analyses will be performed in accordance with the Statistical Analysis Plan. All study data will be listed by treatment, subject and visit (as applicable).

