#### 9.1.2 Analysis of Safety

Analysis of safety data will be presented for all subjects. AEs will be coded using Medical Dictionary for Regulatory Activities (MedDRA, most current version add in version once finalized) and categorized by system organ class using preferred terms. Treatment emergent AEs will be listed by study group. Treatment related AEs will be tabulated by study group and will be reported by incidence (both number of events and number of subjects) with respect to their intensity and relationship to the IP. Ophthalmoscopy findings will be summarized descriptively. IOP measurements, VA, and slit-lamp biomicroscopy assessments will be summarized as safety outcomes.

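### Section 9.6 puts the at-least-one-dose condition on ITT instead of Safety, so a randomized but undosed subject would dilute the adverse event percentages and drop out of ITT

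*Combined protocol and SAP*

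**What the plan says.** Section 9.6 defines three sets:

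- Safety: "The Safety Population will include all randomized subjects". No exposure is required.
- ITT: "The ITT population will include all randomized subjects who took at least 1 dose of investigational product". Exposure is required.
- Per protocol: "The PP population is a subset of the ITT population", so it takes the exposure requirement from ITT.

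Section 9.1.2 says "Analysis of safety data will be presented for all subjects" and does not name a population. It adds that "Treatment related AEs will be tabulated by study group and will be reported by incidence", counting both events and subjects. Section 9.1 supplies the percentage: "Categorical measures will be summarized by the number and percent of subjects". Section 3.1 makes the incidence and severity of treatment-emergent and treatment-related adverse events the primary safety parameter.

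In the causality definitions of section 7.3, the first criterion for an unrelated event is "Event occurring before dosing". Section 3.3 puts the first dose after randomization at Visit 1, observed by unmasked staff.

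**The concern.** A safety set is meant to describe people exposed to the product, and an ITT set is meant to keep everyone who was randomized. Section 9.6 has these the other way round. A subject who is randomized but never receives a drop is counted in Safety and left out of both ITT and the per-protocol set.

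This matters most on the safety side, because adverse event incidence is the primary parameter. The undosed subject cannot have a treatment-related event under the protocol's own causality rule, so including that subject can only lower the percentage. For a safety trial, that is the non-conservative direction. With at most 20 subjects in two arms, one subject is about a tenth of an arm.

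**Working it through.** The documents state no figure that depends on this definition, and section 9.2 says that no formal sample size calculation was made. There is therefore nothing to reproduce. The check has two steps: how the definitions classify an undosed subject, and what that does to a percentage.

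**Classification of a randomized, undosed subject**

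| Rule | Condition | Undosed subject |
|---|---|---|
| Safety (9.6) | randomized | in |
| ITT (9.6) | randomized and dosed | out |
| Per protocol (9.6) | subset of ITT | out |
| Safety presentation (9.1.2) | all subjects | in |
| Treatment-related event (7.3) | not before dosing | cannot occur |

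Whether the denominator is read from 9.6 or from 9.1.2, the undosed subject stays in it.

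**Effect on the percentage**

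Inputs from the documents: up to 20 randomized (9.2) and 1:1 allocation (3.3), hence about 10 per arm at the maximum. Assumptions: the number undosed, u, and the number of subjects with an event, x. The documents give neither.

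The percentage among exposed subjects is x/(n−u). The reported percentage is x/n. Their ratio is (n−u)/n.

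| n | u | x | Exposed | Reported | Difference (points) |
|---|---|---|---|---|---|
| 10 | 0 | 3 | 3/10 = 30.0% | 3/10 = 30.0% | 0 |
| 10 | 1 | 1 | 1/9 = 11.1% | 1/10 = 10.0% | 1.1 |
| 10 | 1 | 3 | 3/9 = 33.3% | 3/10 = 30.0% | 3.3 |
| 10 | 1 | 5 | 5/9 = 55.6% | 5/10 = 50.0% | 5.6 |
| 10 | 2 | 3 | 3/8 = 37.5% | 3/10 = 30.0% | 7.5 |
| 20 (pooled) | 1 | 6 | 6/19 = 31.6% | 6/20 = 30.0% | 1.6 |

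Because 20 is a maximum, arms may be smaller. With u = 1 the ratio is 9/10 = 0.90 at n = 10, 7/8 = 0.875 at n = 8, and 4/5 = 0.80 at n = 5.

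**Effect on what an absence of events can show**

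With no events among m subjects, the exact one-sided 95% upper bound is 1 − 0.05^(1/m). For m = 10 it is 25.9%, and for m = 9 it is 28.3%. The chance of seeing at least one case of an event with a true rate of 10% is 1 − 0.9^m, which is 65.1% for m = 10 and 61.3% for m = 9. Counting one undosed subject as exposed therefore makes the arm look slightly more informative than it is.

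**The case against.** The strongest reply is that the situation is nearly excluded by design. Randomization and first drop happen at the same visit, in the clinic and under supervision (sections 3.3, 3.3.2, 3.3.3 and 5.1.1), so an undosed subject requires something to go wrong within that visit. This stands, and it limits the weight of the point. The cases with two undosed subjects or arms of five are arithmetic illustrations, not expectations. Section 8.1.1.2 does place SD-OCT imaging between randomization and the first drop at some sites, but the list in section 5.1.1 puts imaging before randomization. Little should be built on that interval.

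Second, the affected output is narrow. Event counts, subject counts and listings do not change, efficacy is descriptive, and no analysis section names ITT or the per-protocol set. This also stands: the ITT half of the point is mainly one of labelling. The percentage of subjects with treatment-related events remains a planned summary of the primary parameter, and it does change.

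Third, the Statistical Analysis Plan cited in sections 9.1 and 9.3 might define the sets differently. No such text is among the documents reviewed, so the point is confined to the protocol wording.

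Fourth, adverse events are collected from consent (section 7.2.1), and a dosed-only set would remove an undosed subject's events from the safety summaries. That is true of the summaries, but section 9.1 lists all study data, so the events would still be reported.

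**Conclusion.** The point holds. As written, section 9.6 gives the wrong denominator for treatment-related adverse event percentages whenever a randomized subject is not dosed, and it leaves the same subject out of a set called ITT. Nothing in the documents reviewed corrects it. The understatement is a factor of (n−u)/n. In an arm of 10 with one undosed subject, that is one tenth of the exposed rate, or 1.1 to 5.6 percentage points for one to five subjects with an event. Arm size, number undosed and event counts are assumptions. With no undosed subject the effect is zero, and that is the likeliest outcome. This is an error of definition that should be corrected. It does not threaten the design.

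**What to change.** In section 9.6:

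- Define Safety as all subjects who received at least one dose of the product.
- Define ITT as all randomized subjects, analysed as randomized. If a dosed-only efficacy set is wanted, call it modified ITT.
- Give the per-protocol set its own at-least-one-dose condition, or nest it in modified ITT. It now gets that condition only through ITT and would lose it once ITT is corrected.

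In section 9.1.2, name the Safety set in place of the reference to all subjects, and note that any event in a randomized but undosed subject appears in the listings.

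This takes three sentences in 9.6 and one in 9.1.2, with no cost in data or to patients. The same definitions should appear in the Statistical Analysis Plan. The change should be made before unmasking, because correcting a safety denominator once results are known would look data-driven.

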## **10 DIRECT ACCESS TO SOURCE DATA/DOCUMENTS**

The Investigator will permit trial-related monitoring, audits, IRB review, and regulatory inspection(s) by providing direct access to source data and documents (such as tests performed as a requirement for participation in the study and other medical records required to confirm information contained in the case report form such as medical history) to the monitor.

## **11 QUALITY CONTROL**

The progress of the study will be monitored by on-site, written, e-mail, and telephone communications between personnel at the study center and the sponsor (or designated monitor). The Investigator will allow Tarsius Pharma, Ltd. monitors or designee to inspect all CRFs; subject records (source documents); signed informed consent forms; records of investigational product receipt, storage, and disposition; and regulatory files related to the study.

## 12 ETHICS

### 12.1 INDEPENDENT ETHICS COMMITTEE OR INSTITUTIONAL REVIEW BOARD

The clinical study protocol, protocol amendments, ICF, and all other appropriate study-related documents will be reviewed and approved by an appropriate Independent Ethics Committee (IEC) according to local laws and regulations for study sites outside the United States (US), or Institutional Review Board (IRB) constituted in accordance with US Title 21 Code of Federal Regulations Part 56 for sites in the US. A copy of the letter indicating EC/IRB approval will be provided to Tarsius Pharma, Ltd. (Tarsius) prior to study initiation or implementation of each relevant protocol amendment.

